5.5.3 Vaccine Supply, Storage, and Administration	22
6 STATISTICAL CONSIDERATIONS	22
6.5 SAMPLE SIZE AND POWER ESTIMATION	23
6.6 ANALYSIS PLAN.....	23
6.6.1 Pilot Study	23
6.6.2 Full Study	23
6.7 DATA MANAGEMENT	26
6.7.1 Research Electronic Data Capture (REDCap)	27
6.8 ROLE OF THE CDC INVESTIGATORS IN THE PROJECT	27
7 HUMAN SUBJECTS	28
7.5 HUMAN SUBJECTS INVOLVEMENT, CHARACTERISTICS, AND DESIGN.....	28
7.6 SOURCES OF MATERIAL.....	28
7.7 POTENTIAL RISKS AND BENEFITS	28
7.8 ADEQUACY OF PROTECTION AGAINST RISKS	29
7.8.1 Protections against Risk	29
7.8.2 CLINICALTRIALS.GOV REQUIREMENTS.....	29
7.9 HUMAN SUBJECTS.....	29
7.9.1 Vulnerable Subjects Research	29
REFERENCES	30

PROTOCOL SUMMARY

Title:	A Prospective, Randomized, Open-label Clinical Trial to Assess Apnea Following Administration of 13-valent Conjugate Pneumococcal Vaccine, Diphtheria Toxoid, Tetanus Toxoid, and Acellular Pertussis Vaccine, Inactivated Polio Vaccine, Hepatitis B Vaccine, and Haemophilus influenzae Type B Vaccine in Preterm Infants
Phase:	Phase 4
Population:	Up to 300 premature infants <33 weeks and 0 days gestational age and 6-12 weeks postnatal age who will receive 13-valent Conjugate Pneumococcal Vaccine (PCV13), Diphtheria Toxoid, Tetanus Toxoid, and Acellular Pertussis Vaccine (DTaP), Hepatitis B vaccine (HBV), and Haemophilus influenzae Type B Vaccine (Hib)
Clinical Sites:	Three: Duke University (Lead); University of North Carolina (Lead Subcontractor); Cincinnati Children’s (Contributing)
Study Duration:	28 months
Participant Duration:	Up to 14 days
Description of Study Procedures:	This is a prospective, randomized, open-label clinical trial. Infants will be randomized (1:1) to receive either simultaneous administration of PCV13, DTaP, HBV, IPV, and Hib vaccines or no vaccination. Unvaccinated infants will be followed for 48 hours after randomization to capture episodes of apnea. Vaccinated infants will be followed for 48 hours after vaccination for apnea. In addition, vaccinated infants will be followed for 14 days after vaccination for adverse events using information documented in the medical record or obtained by phone call to the parent/legally authorized representative (LAR) on day 14.
Objectives:	
Primary Objective (PO): PO 1: To compare proportions of preterm infants with apnea in a 48-hour monitoring period after vaccination in the “vaccinated” group versus a 48-hour monitoring period after randomization in the “unvaccinated” group.
 
The primary hypothesis is that the proportion of infants with apnea will be higher in the “vaccinated” group compared to the “unvaccinated” group.
 
Secondary Objectives (SO): SO 1: To compare the clinical importance of apneic events in a 48-hour monitoring period after vaccination in the “vaccinated” group versus a 48-hour monitoring period after randomization in the “unvaccinated” group. SO 2: To compare proportions of preterm infants with severe cardiorespiratory events in a 48-hour monitoring period after vaccination in the “vaccinated” group versus a 48-hour monitoring period after randomization in the “unvaccinated” group.
 
Exploratory Objectives (EO): EO 1: To compare proportions of preterm infants with temperature instability in a 48-hour monitoring period after vaccination in the “vaccinated” group versus a 48-hour monitoring period after randomization in the “unvaccinated” group.

	
EO 2: To compare proportions of preterm infants with other clinically important adverse events in a 48-hour monitoring period after vaccination in the “vaccinated” group versus a 48-hour monitoring period after randomization in the “unvaccinated” group.
 
EO 3: To compare clinically important adverse events occurring between 48 hours and 14 days after vaccination among infants in the vaccinated group who do, and do not have apnea in a 48-hour monitoring period after vaccination.


Outcome Measures:
	
Primary Outcome Measure (POM): POM 1.1: Proportion of infants with ≥ 1 apneic event in a 48-hour monitoring period after vaccination in the “vaccinated” group and a 48-hour monitoring period after randomization in the “unvaccinated” group.
 
Secondary Outcome Measures (SOM): SOM 1.1: Average number of apneic episodes in a 48-hour monitoring period after vaccination in the “vaccinated” group and a 48-hour monitoring period after randomization in the “unvaccinated” group. SOM 1.2: Average duration of apneic episodes in a 48-hour monitoring period after vaccination in the “vaccinated” group and a 48-hour monitoring period after randomization in the “unvaccinated” group. SOM 1.3: Proportion of infants requiring any increase in respiratory support in a 48-hour monitoring period after vaccination in the “vaccinated” group and a 48-hour monitoring period after randomization in the “unvaccinated” group. SOM 2.1: Proportion of infants with ≥ 1 severe cardiorespiratory event in a 48-hour monitoring period after vaccination in the “vaccinated” group and a 48-hour monitoring period after randomization in the “unvaccinated” group. SOM 2.2: Proportion of infants requiring positive pressure ventilation in a 48-hour monitoring period after vaccination in the “vaccinated” group and a 48-hour monitoring period after randomization in the “unvaccinated” group.
 
Exploratory Outcome Measures (EOM): EOM 1.1: Proportion of infants with fever in a 48-hour monitoring period after vaccination in the “vaccinated” group and a 48-hour monitoring period after randomization in the “unvaccinated” group. EOM 1.2: Proportion of infants with hypothermia in a 48-hour monitoring period after vaccination in the “vaccinated” group and a 48-hour monitoring period after randomization in the “unvaccinated” group. EOM 2.1: Average number of oxygen desaturation events in a 48-hour monitoring period after vaccination in the “vaccinated” group and a 48-hour monitoring period after randomization in the “unvaccinated” group. EOM 2.2: Average number of bradycardia events in a 48-hour monitoring period after vaccination in the “vaccinated” group and a 48-hour monitoring period after randomization in the “unvaccinated” group. EOM 2.3: Proportion of infants requiring blood culture for and/or antibiotics (intravenously or intramuscularly) in the setting of blood culture for sepsis evaluation in a 48-hour monitoring period after vaccination in the “vaccinated” group and a 48-hour monitoring period after randomization in the “unvaccinated” group.


	
EOM 2.4: Proportion of infants with a serious adverse event in a 48-hour monitoring period after vaccination in the “vaccinated” group and a 48-hour monitoring period after randomization in the “unvaccinated” group.
 
EOM 3.1: Proportion of hospitalized infants with ≥ 1 episode of clinical apnea between 48 hours and 14 days after vaccination.
 
EOM 3.2: Proportion of hospitalized infants requiring any increase in respiratory support between 48 hours and 14 days after vaccination.
 
EOM 3.3: Proportion of hospitalized infants requiring blood culture and/or antibiotics (intravenously or intramuscularly) in the setting of blood culture for sepsis evaluation in between 48 hours and 14 days after vaccination.
 
EOM 3.4: Proportion of hospitalized infants requiring positive pressure ventilation in between 48 hours and 14 days after vaccination.
 
EOM 3.5: Proportion of discharged infants readmitted to the hospital within 14 days of vaccination.

Estimated Time to Complete Enrollment:	Approximately 28 months

1 BACKGROUND

1.1 Background

Premature infants (<37 weeks gestational age at birth) are at high risk for undervaccination. Despite concerns regarding the immaturity of the premature infant immune system, the majority of premature infants achieve antibody concentrations generally accepted to correlate with protection.¹ The Centers for Disease Control and Prevention Advisory Committee on Immunization Practices (ACIP) and the American Academy of Pediatrics have thus recommended that in most cases with the exception of hepatitis B vaccine, premature infants should receive all routinely recommended vaccines at the same chronological age as term infants.² Despite this recommendation, premature infants have been shown to be underimmunized at 6 months,³ 12 months,^{3,4} 24 months,⁵ and 36 months⁶ chronological age. Infants who are discharged from the neonatal intensive care unit (NICU) after lengths of stay ≥ 60 days are at particularly high risk, with only approximately 50% up-to-date at the time of discharge.⁷ Vaccination delay at this earlier age thus contributes to undervaccination at later ages.

Premature infants are underimmunized for multiple reasons. In the general healthy infant population, vaccination rates are linked to a variety of factors, including socioeconomic status,⁸ parental anxiety,⁸ and young maternal age.⁹ While these issues still may play a role for premature infants, especially considering the increased burden of prematurity among mothers of low socioeconomic status,¹⁰ it is clear that additional factors have an impact on vaccination rates for premature infants hospitalized in the NICU. Some studies have shown lower birth weight to be a risk factor for undervaccination,^{5,6} possibly indicating that more critical disease status may affect the decision to administer vaccines. On the contrary, diagnoses of congenital heart disease and bronchopulmonary dysplasia were associated with increased vaccination rates in another study of infants discharged from the NICU.⁷ It is likely that factors affecting vaccination rates vary according to geographic region and individual NICU.

The perceived risk of reappearance or worsening of apnea after vaccination in premature infants likely contributes to undervaccination. Apnea is a common symptom noted in the NICU in the presence or absence of vaccination due to apnea of prematurity. Apnea of prematurity is a developmental disorder characterized by cessation of breathing and often accompanied by bradycardia, cyanosis, or pallor. Apneic events can be divided into 3 subtypes: central (failure of the infant to initiate a breath; obstructive (related to pharyngeal obstruction); and mixed (combination of central and obstructive). The pathogenesis of apnea of prematurity involves persistence of immature reflexes and immature responses to hypoxia and hypercapnia. The incidence of apnea is inversely proportional to the gestational age (GA) at birth, with essentially all infants ≤ 28 weeks' gestation diagnosed with apnea and 20% of those born at 34 weeks' gestation.¹¹ Most, but not all, of the U.S. Food and Drug Administration labels for the commonly administered infant vaccines mention premature infants (**Table 1**). While none of the vaccinations are specifically indicated in premature infants, several labels provide warnings that advise of the risk of apnea following vaccination in premature infants (**Table 1**). Awareness of this potential risk has originated from a number of retrospective and observational studies that have evaluated vaccination safety in premature infants (**Table 2**). The incidence of cardiorespiratory events (i.e. apnea and/or bradycardia) following vaccination ranged from 0-47% in these studies. Risk factors for cardiorespiratory events in some studies included lower gestational age and higher clinical disease severity (such as longer period of ventilation and presence of chronic lung disease). In several of these studies, infants served as their own controls, as they were observed pre-vaccination.

The relationship between vaccination and apnea has been studied extensively but the evidence is inconclusive for a causal association. While retrospective and prospective observational studies suggest a possible link between vaccination and apnea in premature infants, there are several inherent problems with these studies. Each study examines different

combinations of vaccinations, and they commonly have small sample sizes, use retrospective data, and vary in inclusion criteria and definition of adverse events. Observational studies that use immunized infants as their own controls also have an important flaw: clinicians are most likely to immunize an infant at a period of high stability. Thus, a small window of time prior to vaccination is likely to contain fewer cardiorespiratory events. After vaccination, infants may experience events associated with prematurity and disease status. Only one randomized controlled trial has been performed and showed no difference in prolonged apneic events between the immunized and control groups.¹² Infants in this study were enrolled at 56-60 days postnatal age. However, some infants in this study received DTaP alone, while others received DTaP-HBV-IPV. The variability in the evidence makes it inconclusive if the apnea described after vaccination in preterm infants is vaccine-related or a complication of underlying prematurity.

Table 1. U.S. FDA labels for routine infant immunizations: indications and warnings for premature infants.

Immunization brand name	Component vaccines	Specific indication for premature infants	Warning in label for premature infants
Pediarix ¹³	Diphtheria, tetanus, and acellular pertussis Hepatitis B recombinant Inactivated poliovirus	No	“Apnea following intramuscular vaccination has been observed in some infants born prematurely. Decisions about when to administer an intramuscular vaccine, including PEDIARIX, to infants born prematurely should be based on consideration of the individual infant’s medical status, and the potential benefits and possible risks of vaccination.”
Pentacel ¹⁴	Diphtheria, tetanus, and acellular pertussis Inactivated poliovirus Haemophilus b conjugate	No	“Apnea following intramuscular vaccination has been observed in some infants born prematurely. The decision about when to administer an intramuscular vaccine, including Pentacel, to an infant born prematurely should be based on consideration of the individual infant’s medical status and the potential benefits and possible risks of vaccination. The potential risk of apnea and the need for respiratory monitoring for 48 – 72 hours should be considered when administering the primary immunization series to very premature infants (born ≤ 28 weeks of gestation) and particularly for those with a previous history of respiratory immaturity. As the benefit of vaccination is high in this group of infants, vaccination should not be withheld or delayed.”
Pevnar-13 ¹⁵	Pneumococcal 13-valent conjugate	No	“Apnea following intramuscular vaccination has been observed in some infants born prematurely. Decisions about when to administer an intramuscular vaccine, including Pevnar 13, to infants born prematurely should be based on consideration of the individual infant’s medical status, and the potential benefits and possible risks of vaccination.”
ActHIB ¹⁶	Haemophilus b conjugate	No	None
Engenerix-B ¹⁷	Hepatitis B recombinant	No	“The potential risk of apnea and the need for respiratory monitoring for 48 to 72 hours should be considered when administering the primary immunization series to very premature infants (born ≤28 weeks of gestation) who remain hospitalized at the time of vaccination and particularly for those with a previous history of respiratory immaturity. It is generally understood that the benefit of vaccination is high in very premature infants. The decision to vaccinate should be based

			on careful consideration of the potential benefits and possible risks.”
--	--	--	---

Table 2. Evidence of adverse cardiorespiratory events (including apnea) after immunization in premature infants.¹

Immunization	Study design	N	Mean gestational age (weeks)	Cardiorespiratory (apnea and/or bradycardia) events	Follow-up	Factors associated with events
DTwP ¹⁸	Retrospective	97	28	20%	24 hours	Younger gestational age Longer ventilation Chronic lung disease
DTwP ± Hib ¹⁹	Prospective observational	98	27	17%	24 hours	Receipt of DTwP alone
Hib, HBV, DTaP, IPV ²⁰	Retrospective	48	26	0%	48 hours	N/A
DTwP+Hib ²¹	Prospective observational	97	27	12%	72 hours	Lower weight More severe apnea of prematurity Chronic lung disease
DTwP, Hib, HBV ²²	Prospective observational	79	28	30%	24 hours	N/A
DTaP, IPV, Hib ²³	Retrospective observational	78	28	47%	48 hours	Severe clinical course Persistence of cardiorespiratory symptoms at time of immunization
DTaP, IPV, Hib, HBV ²⁴	Retrospective	53	28	13%	72 hours	N/A
DTaP ¹²	Randomized controlled	191	27	“Prolonged apnea” 16%: DTaP group 20%: control group	48 hours	N/A
DTaP, IPV, Hib, HBV ²⁵	Prospective observational	45	27	11%	72 hours	Chronic diseases
Multiple, including HBV, DTaP, Hib, OPV ²⁶	Retrospective	411	27	5%	7 days	Previous sepsis Longer prior duration of CPAP
Multiple, including HBV, DTaP, Hib, IPV, OPV, Strep pneumo, influenza ²⁷	Retrospective	497	Not provided	13%	48 hours	Younger postnatal age Lower birth weight More severe clinical illness

DTaP, IPV, Hib or DTwP, IPV, HiB ²⁸	Retrospective	124	27	45%	72 hours	Lower weight
DTaP, Hib, meningococcal serogroup C ²⁹	Retrospective	76	27	38%	24 hours	N/A

DTwP=diphtheria, tetanus, whole cellular pertussis; DTaP=Diphtheria, tetanus, acellular pertussis; HBV = hepatitis B virus; Hib = *Haemophilus influenzae* type B; IPV=inactivated poliovirus; OPV=oral poliovirus.

1.2 Summary & Rationale

Premature infants are at high risk for apnea. Current published recommendations state that this group of infants should receive vaccinations according to chronological age, but frequently this does not occur. Clinicians often delay administration of vaccinations due to concern about the reappearance or worsening of apnea, but evidence to support a causal association is inconclusive. Further study is warranted to quantify the risk and clinical importance of apnea in premature infants after vaccination.

We therefore propose to conduct a randomized clinical trial to assess the risk of apnea in premature infants following routine vaccination. In addition, the study would provide more information about other adverse events following vaccination in the context of current US childhood vaccination practices. This study will provide evidence about the risk and clinical importance of apnea after vaccination in preterm infants and will broaden understanding of adverse events after vaccination in the context of current US vaccination practices. A better understanding of the safety of routine vaccination in preterm infants will assist with clinical decision-making and anticipatory guidance to parents which may improve timely vaccination in preterm infants. Information from this study will also help guide future research efforts to identify potential risk factors and prevention strategies for apnea after vaccination.

2 STUDY OBJECTIVES

Primary Objective (PO):

PO 1: To compare proportions of preterm infants with apnea in a 48-hour monitoring period after vaccination in the “vaccinated” group versus a 48-hour monitoring period after randomization in the “unvaccinated” group.

The primary hypothesis is that the proportion of infants with apnea will be higher in the “vaccinated” group compared to the “unvaccinated” group.

Secondary Objectives (SO):

SO 1: To compare the clinical importance of apneic events in a 48-hour monitoring period after vaccination in the “vaccinated” group versus a 48-hour monitoring period after randomization in the “unvaccinated” group.

SO 2: To compare proportions of preterm infants with severe cardiorespiratory events in a 48-hour monitoring period after vaccination in the “vaccinated” group versus a 48-hour monitoring period after randomization in the “unvaccinated” group.

Exploratory Objectives (EO):

EO 1: To compare proportions of preterm infants with temperature instability in a 48-hour monitoring period after vaccination in the “vaccinated” group versus a 48-hour monitoring period after randomization in the “unvaccinated” group.

EO 2: To compare proportions of preterm infants with other clinically important adverse events in a 48-hour monitoring period after vaccination in the “vaccinated” group versus a 48-hour monitoring period after randomization in the “unvaccinated” group.

EO 3: To compare clinically important adverse events occurring between 48 hours and 14 days after vaccination among infants in the vaccinated group who do, and do not have apnea in a 48-hour monitoring period after vaccination.

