Exploratory Objective 1 - To compare proportions of preterm infants with temperature instability in a 48-hour monitoring period after vaccination in the “vaccinated” group versus a 48-hour monitoring period after randomization in the “unvaccinated” group.

For this objective we will present the proportion of infants the proportion of infants in each group experiencing fever and the proportion in each group experiencing hypothermia (as defined in Section A.5.3) at least once during the 48 hours after randomization/vaccination and compare these proportions using a Mantel-Haenszel statistic.

Exploratory Objective 2 - To compare proportions of preterm infants with other clinically important adverse events in a 48-hour monitoring period after vaccination in the “vaccinated” group versus a 48-hour monitoring period after randomization in the “unvaccinated” group.

For this objective we will present the proportion of infants the proportion of infants in each group experiencing other clinically important adverse events (as defined in Section A.5.3) at least once during the 48 hours after randomization/vaccination and compare these proportions using a Mantel-Haenszel statistic. We will repeat these analyses for serious adverse events. We will report SAE narratives and relatedness descriptions (see section 5.3).

Exploratory Objective 3 - To compare clinically important adverse events occurring between 48 hours and 14 days after vaccination among infants in the vaccinated group who do, and do not have apnea in a 48-hour monitoring period after vaccination.

For this objective we will present the proportion of infants in the vaccinated group with and without apnea in a 48-hour monitoring period who experience each of these clinically important adverse events (as defined in section A.5.3) at least once between 48 hours and 14 days after vaccination. These subgroup comparisons will be conducted a Fisher’s Exact Test at the alpha 0.05 level.

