### 4.3 Randomization

Participants will be randomized (1:1) to either vaccinated or unvaccinated groups using a permuted block randomization scheme stratified by gestational age (<28 weeks, ≥28 weeks) and study site (i.e. Duke University Medical Center, University of North Carolina at Chapel Hill Hospital, and Cincinnati Children's Hospital Medical Center). Infants randomized to the vaccinated group should receive vaccines within 6 hours but will be allowed to receive vaccines up to 12 hours post-randomization. The first 12 infants enrolled in the Pilot Phase I will be randomized in a separate permuted block by manual randomization (e.g., envelopes). The project statistician at Duke University will generate permuted block randomization schemes, which will be uploaded to REDCap for the full study. The randomization schedule will not be available to the study staff, so the next randomization allocation will not be known before randomization occurs. Following confirmation of study eligibility criteria, participant randomization will be through REDCap with treatment arm allocation recorded on the case report form. In the event that REDCap is unavailable, manual randomization will occur through the use of envelopes. The project statistician will prepare 20 envelopes per site that will use the same randomization strategy as the primary scheme embedded in REDCap. When manually randomizing, the team member will pull the next envelope in order. In order to capture the allocation per subject, a separate form in REDCap will be used by the personnel to add the assignment. A log will need to be kept at the site capturing these instances.

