## 7 BASELINE DATA AND FLOW CHART

### 7.1 Presentation of Baseline Data

The following baseline data will be presented by site and vaccination group: age, birthweight, sex, gestational age (median, range and number and percentages <28 weeks and ≥28 weeks gestational age), multiple gestation, reason for preterm delivery, insurance payer status, ethnicity, race, whether sibling currently enrolled or previously enrolled in this study, and medical conditions since birth (including intraventricular hemorrhage, necrotizing enterocolitis, periventricular leukomalacia, seizures, and apnea of prematurity), postnatal age on the day of randomization, postmenstrual age on the day of randomization, respiratory support and supplemental oxygen use on the day of randomization, caffeine use on the day of randomization, and receipt of Synagis or other procedures during the study period. Summary statistics (e.g., mean, median, standard deviation, interquartile range) will be presented for continuous variables. Categorical variables will be described with frequencies and percentages.

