proportions will be compared using a Mantel-Haenszel statistic in a stratified analysis by study site and gestational age to control for the randomization blocks. The stratified odds ratio and corresponding 95% confidence interval for the occurrence of these outcome measures will also be calculated. We will provide a listing of SAE narratives and relatedness descriptions.

- c) The third exploratory objective (**EO-3**) is to compare clinically important adverse events occurring between 48 hours and 14 days after vaccination among infants in the vaccinated group who do / do not have apnea in a 48-hour monitoring period after vaccination.

For this objective the proportion of infants in the vaccinated group with and without apnea in a 48-hour monitoring period who experience each of the clinically important adverse events listed below at least once between 48 hours and 14 days after vaccination will be presented.

- $\geq 1$  episode of clinical apnea in hospitalized infants (EOM 3.1)
- any increase in respiratory support in hospitalized infants (EOM3.2)
- blood culture and/or antibiotics (intravenously or intramuscularly) in the setting of blood culture for sepsis evaluation in hospitalized infants (EOM 3.3)
- positive pressure ventilation in hospitalized infants (EOM 3.4)
- readmission to the hospital within 14 days of vaccination in discharged infants (EOM 3.5)

These subgroup comparisons will be made using a Mantel-Haenszel statistic in a stratified analysis by study site and gestational age to control for the randomization blocks at the two-sided alpha 0.05 level. The stratified odds ratio and corresponding 95% confidence interval for the occurrence of these outcome measures will also be calculated.

No adjustments will be made to the alpha level (two-sided alpha=0.05) for these exploratory analyses.

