#### **8.4 Postmenstrual age (PMA) Evaluation**

Study objectives PO1, SO1, SO2, EO2.1, EO2.2, EO3.1, and EO3.2 will be presented and evaluated between groups by postmenstrual age group (PMA <37 weeks /  $\geq$ 37 weeks). PMA will be defined as the sum of gestational age plus postnatal age. PO1, SO2, and EO3 are categorical with either no event or 1 or more events, and will be presented and compared using a Mantel- Haenszel statistic by PMA group at the two-sided alpha 0.05 level. The stratified odds ratio and corresponding 95% confidence interval for the occurrence will also be calculated. SO1 and EO2 are count data and will be compared using a Poisson regression model with study site as covariates by PMA group. These tests will be performed at the alpha 0.05 level.

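### EO 3 compares non-randomized groups with no adjustment for clinical severity, so its odds ratio tends above 1 even if early apnea has no consequence; it should be labelled an association and supplemented by baseline respiratory support

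*Protocol*

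**What the plan says.** - **Contrast.** Protocol section 2 compares later events "among infants in the vaccinated group who do, and do not have apnea in a 48-hour monitoring period after vaccination". The outcomes, EOM 3.1–3.5, are clinical apnea, increased respiratory support, blood culture or antibiotics for sepsis evaluation, positive pressure ventilation, and readmission. EOM 3.1–3.4 are confined to hospitalized infants.
- **Test, protocol.** Section 6.2.2.3: "These subgroup comparisons will be conducted a Fisher’s Exact Test at the alpha 0.05 level". No covariate enters.
- **Test, SAP.** Section 8.3(c): the comparisons are "made using a Mantel-Haenszel statistic in a stratified analysis by study site and gestational age to control for the randomization blocks". Randomization was "stratified by gestational age (<28 weeks, ≥28 weeks) and study site" (SAP 4.3), so gestational age has two levels. Each test is at two-sided 0.05, unadjusted.
- **Additional split.** SAP 8.4 includes EO 3.1 and EO 3.2 among the results examined by postmenstrual age (below 37 weeks, 37 weeks or more).
- **Severity.** Protocol 1.1: "Risk factors for cardiorespiratory events in some studies included lower gestational age and higher clinical disease severity", with longer ventilation and chronic lung disease as examples. Table 2 of the protocol repeats the pattern across several cited studies.
- **Severity data held.** SAP 7.1 presents "respiratory support and supplemental oxygen use on the day of randomization, caffeine use on the day of randomization" as baseline data. Protocol 5.4 records respiratory support at vaccination for the vaccinated group. Neither document uses any of this in EO 3.
- **No later control.** Unvaccinated infants leave the study at 48 hours (protocol 5.2).

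**The concern.** The SAP carries the stratified method of the randomized comparisons over to a contrast that was not randomized. Every infant in EO 3 is in the vaccinated arm, and the grouping variable is itself an outcome. Stratifying by site and gestational age may still be sensible, because both could relate to apnea and to later events, but the stated reason does not apply. What matters here is confounding, and the confounder the protocol itself points to is left out.

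Infants on CPAP, on nasal cannula or on no support can all enter the trial; only mechanical ventilation and NIPPV exclude. Baseline severity will therefore vary within the vaccinated arm. If the sicker infants have more early apnea and also more later events, the two will be associated even when one has no bearing on the other.

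At stake is how the result is read. Protocol 1.2 says the trial is meant to inform clinical decisions and what parents are told, against a background of vaccination being delayed for fear of apnea. An unqualified odds ratio above 1 could be taken to show that vaccine-related apnea leads to harm. No unvaccinated infant is followed past 48 hours to check that reading.

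**Working it through.** **1. The plan's own figures.** For 15% v 30%, 135 per group and a two-sided 0.05 chi-square test with pooled variance, power is 84.32%, which reproduces the stated 84.3%. Dropout: 270 / (1 − 0.10) = 300, also as stated. The documents give no event rate, power or sample size for EO 3.

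**2. Group sizes in EO 3.** At 30% apnea, 135 × 0.30 = 40.5 infants with early apnea and 94.5 without. With 150 infants the figures are 45 and 105. On the plan's assumptions, 0.15 / 0.30 = one half of the early apnea in the vaccinated arm would have occurred without vaccination.

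**3. What confounding does to the planned odds ratio.** Let early apnea have no effect on later events, and let a binary severity factor S raise both. Within each gestational-age stratum, with A and Y denoting early apnea and a later event,

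P(A, Y) = Σ over S of P(S) × P(A given S) × P(Y given S),

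and likewise for the other three cells. The large-sample Mantel-Haenszel odds ratio is the sum over strata of P(A,Y) × P(not A, not Y), divided by the sum of P(A, not Y) × P(not A, Y). The two gestational-age strata have equal weight here.

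*Worked case, strong assumptions.* S is respiratory support at baseline: 55% below 28 weeks, 25% at 28 weeks or more. Apnea is 50% v 17% and later events 40% v 10%, with v without support. The implied severity odds ratios are (0.50/0.50)/(0.17/0.83) = 4.9 and (0.40/0.60)/(0.10/0.90) = 6.0.

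| Stratum | A,Y | A, not Y | not A, Y | neither |
|---|---|---|---|---|
| <28 weeks | 0.11765 | 0.23385 | 0.14735 | 0.50115 |
| ≥28 weeks | 0.06275 | 0.18975 | 0.11225 | 0.63525 |

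Numerator: 0.11765 × 0.50115 + 0.06275 × 0.63525 = 0.05896 + 0.03986 = 0.09882.
Denominator: 0.23385 × 0.14735 + 0.18975 × 0.11225 = 0.03446 + 0.02130 = 0.05576.
Odds ratio: 0.09882 / 0.05576 = 1.77, although the true effect is nil.

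*Weaker version of the same case.* Apnea 42% v 22% and later events 30% v 10% (severity odds ratios 2.6 and 3.9) give (0.04270 + 0.03014) / (0.03280 + 0.02264) = 1.31.

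**4. Range of assumptions, with rejection rates.** Simulation of the Mantel-Haenszel test stratified by three sites and two gestational-age levels, with no true effect. The grid rows use 4,000 trials per setting with 135 or 150 infants, severity present in 30–50% of infants, later events in 10–30%, and gestational-age odds ratios of 2. All rows assume site shares of 30/30/40% and half the infants below 28 weeks. The last two rows are the cases in step 3, with 135 infants.

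| Severity odds ratio on apnea / later event | Mantel-Haenszel odds ratio | Rejection, nominal 5% test |
|---|---|---|
| 2 / 2 | 1.11–1.12 | 5.2–6.4% |
| 3 / 3 | 1.30–1.33 | 7.3–11.9% |
| 4 / 4 | 1.48–1.56 | 11.1–19.7% |
| 2.6 / 3.9 | 1.3 | about 9–10% |
| 4.9 / 6.0 | 1.8 | about 25% |

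Adding S as a further stratum returns rejection to about 4–6%. This follows by construction, because S is the only confounder left out of the planned strata. It shows what adjustment does when severity is captured by the added variable; it does not show that respiratory support captures all of severity.

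**5. Scale.** With about 40–45 infants with apnea, 80% power needs an odds ratio of roughly 2.8 to 5.3 for later-event rates of 30% down to 5% in infants without apnea.

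**The case against.** The strongest reply is that the plan states no causal question. EO 3 is exploratory and worded as a comparison. As prognosis (do infants with apnea after vaccination go on to have more events?), the association is informative even if severity explains all of it, and informing parents is a stated aim. The clinical importance of apnea is addressed by randomized comparisons under SO 1 and SO 2. This stands: the odds ratio misleads only when read causally, and the stratified result is worth keeping as a description.

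A reader might infer that the design will produce a false link, or that a significant result is to be expected under no effect. The documents do not support that. They give no effect sizes, and even the strongest assumptions above leave about three trials in four non-significant. With severity odds ratios of 2 the distortion is slight. Eligibility also narrows the range of severity, by excluding ventilated infants and those under treatment for active infection and by requiring the clinician to judge the infant ready for vaccination.

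SAP 8.4 does examine EO 3.1 and EO 3.2 by postmenstrual age. That is maturity rather than severity, and EOM 3.3–3.5 are not covered.

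None of this supplies a reason for the randomization-blocks wording, explains why two different tests are specified, or tells the reader that the result is only prognostic.

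**Conclusion.** The point holds as a limit on interpretation and a gap in the EO 3 analysis. The groups are not randomized, the protocol and SAP specify different tests, the SAP's reason for stratifying does not apply, and no severity measure enters although the protocol links severity to the grouping event. If severity raises both early apnea and later events, the planned odds ratio lies above 1 under no effect: about 1.1 to 1.5 for assumed severity odds ratios of 2 to 4, and about 1.8 for roughly 5 and 6. The direction rests on that one premise; the size rests on assumed inputs and is unknown. The protocol's unadjusted Fisher test also leaves any gestational-age or site confounding in place. The primary and secondary randomized comparisons are untouched.

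**What to change.** 1. Reconcile protocol 6.2.2.3 (Fisher's exact) with SAP 8.3(c) (Mantel-Haenszel), so that one test is specified for EO 3.
2. Keep the analysis stratified by site and gestational age as the descriptive, prognostic result, and delete the randomization-blocks rationale for EO 3.
3. For EOM 3.1–3.5, add an analysis further stratified by, or adjusted for, baseline respiratory support (any v none), using the value recorded at vaccination. Add caffeine and postmenstrual age only where event counts allow. Penalized logistic regression that retains site is one option.
4. State in the SAP and in the report that EO 3 is an association within vaccinated infants, not an effect of vaccination or of vaccine-related apnea.

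The cost is SAP wording and one further analysis per outcome, from data already collected. With about 40–45 infants with apnea, intervals will be somewhat wider and few covariates can be supported. Residual confounding remains, as does selection from confining EOM 3.1–3.4 to hospitalized infants, since time to discharge may itself depend on severity; the report should say so.
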